## 2. INTRODUCTION

Hemophilia A and B are chronic inherited bleedings disorders caused by an X-chromosome linked deficiency in coagulation factors. Although the incidence of hemophilia is relatively low, it imposes a high level of burden to sufferers, caregivers, and society. As hemophilia requires lifetime treatment it is associated with substantial costs, particularly direct costs. Factor replacement therapy, used for both prophylaxis and on-demand therapy, is the mainstay of hemophilia treatment and has been estimated to cost more than \$250,000 per adult in the United States. Depending on the disease severity and treatment regimen, factor replacement products accounts for 45% to 93% of the total medical costs for hemophilia.

Newer, longer acting treatments for hemophilia have recently been approved by the FDA. Alprolix is a longer-acting treatment than traditional treatments that was approved by the FDA in March, 2014 for hemophilia B. And similarly, for hemophilia A, Eloctate was approved in 2014 and Adynovate in 2015. These newer, longer-acting drugs require less frequent administrations than Pfizer's BeneFIX (for hemophilia B) and Xyntha (for hemophilia A). Even a relatively small change in frequency of administration has the potential to translate into 50 or fewer infusions per year and a correspondingly smaller number of units infused per patient. The expected advantages of fewer infusions from longer acting products include greater patient compliance, less disruptions in daily activities and less reliance on others to help with infusions. However; these benefits are only realized if there is indeed fewer infusions associated with the longer-acting products compared with the shorter-acting products. To date, little is known about real world administration patterns for longer-acting treatments in comparison to traditional treatments. Pfizer is seeking to generate evidence which validates the hypothesis they have that Alprolix , Eloctate, and Adynovate are being dosed more often than their labeling indicates, thus potentially costing payors and patients more money compared to traditional treatments, like BeneFIX and Xyntha.

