### ***6.1.3. Multivariable Analyses***

#### Generalized Linear Models

The type of GLM will be chosen on the basis of the distributions of the outcome variables of interest. For example, GLMs specifying a normal distribution and identity function will be used with mostly normally distributed variables (such as is typically the case with SF-36v2 HRQoL measures), whereas GLMs specifying a negative binomial distribution and log-link function will be used with highly positively skewed variables (such as is typically the case with healthcare resource utilization measures). Model fits will be examined to aid with model selection. For example, Poisson models may be attempted first, with highly skewed outcomes, but negative binomial models will also be tested to see if fits improve substantially when including the estimated relationship between mean and variance. Corrections to the standard errors will be implemented automatically to compensate for model underdispersion. In the case of normal distributions, GLMs are recommended, as they are more robust than ordinary least squares (OLS) models to minor deviations from normality.

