### 6.2.3. Multivariable Analyses

For hemophilia A and hemophilia B cohorts separately, multivariable regression models will be conducted with treatment group (standard half-life vs. extended half-life) as the predictor of each outcome (ie, number of infusions, health-related quality of life, healthcare resource utilization, total healthcare costs, total Rx costs, hemophilia healthcare costs, hemophilia Rx costs) adjusting for the demographic and health history variables that have been identified as relevant covariates in bivariate analyses.

Generalized linear models will be used specifying the appropriate distribution (ie, negative binomial for skewed variables such as healthcare resource use and cost variables; identity link function for normally distributed variables such as health-related quality life). A regression summary results table with adjusted means, 95% CIs, standard errors, and p-values will be produced ([Table 8](#)).

**Table 8. Example regression summary table. Outcomes among hemophilia A patients by standard half-life vs. extended half-life treatment (adjusted for covariates). Note: a similar table would be created for hemophilia B patients.**

Outcome	Standard Half-Life				Extended Half-Life				p-value
	Mean	SE	Lower 95% CI	Upper 95% CI	Mean	SE	Lower 95% CI	Upper 95% CI	
Number of infusions per month									
SF-36 MCS/ SF-10 psychosocial									
SF-36 PCS / SF-10 physical									
HEAM-A-QOL / HAEMO-QOL									
Total Healthcare visits									
Total Healthcare costs									
Total Rx costs									
Hemophilia healthcare visits									
Hemophilia healthcare costs									
Hemophilia Rx costs									

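### SAP 6.2.3 gives the four cost outcomes a count model, with no standard error that holds if costs have heavier tails than gamma or include zeros

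*SAP*

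**What the plan says.** SAP 6.2.3 (Multivariable Analyses) introduces its choice of family with 'ie' and assigns the "negative binomial for skewed variables such as healthcare resource use and cost variables". Its list of modelled outcomes includes "total healthcare costs, total Rx costs, hemophilia healthcare costs, hemophilia Rx costs) adjusting for the demographic and health history variables". That is four cost outcomes per hemophilia type, each with a row in Table 8 giving adjusted means, standard errors, 95% intervals and a p-value.

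SAP 6.1.3 (repeated in Protocol 8.7) is more general. It states "The type of GLM will be chosen on the basis of the distributions of the outcome variables of interest" and "Model fits will be examined to aid with model selection". For skewed outcomes it says that "GLMs specifying a negative binomial distribution and log-link function will be used with highly positively skewed variables", with resource utilization, not cost, as the example. Poisson is the only other family it mentions for such data, and the two are compared "to see if fits improve substantially when including the estimated relationship between mean and variance". On standard errors it says only: "Corrections to the standard errors will be implemented automatically to compensate for model underdispersion".

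Neither section names a continuous skewed family, a robust standard error, a Pearson scale for overdispersion, the currency unit, the dispersion estimator or the handling of zero costs. The only cost level in the documents is in the SAP introduction, where factor replacement "has been estimated to cost more than \$250,000 per adult in the United States". No SD is given.

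**The concern.** The negative binomial is a distribution for non-negative integers with variance μ + αμ². Costs are continuous amounts. They may have heavier tails than this form allows, and some may be zero. The model-based standard error is right only if the fitted variance matches the true one. Because the variance mixes a linear and a quadratic term, the fit is not invariant to the unit in which cost is recorded.

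Four of the ten Table 8 rows per hemophilia type are costs, and resource utilization is part of the primary objective. The SAP introduction also says that the sponsor hopes to confirm that extended half-life products may cost payors more. Intervals that are too narrow would produce false cost differences between treatment groups; intervals that are too wide would hide real ones.

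**Working it through.** **Inputs.** From the SAP: 75 per group and two-sided α = 0.05 (section 2.2), and mean cost of about USD 250,000 (section 2). Assumed: tail shape, CV or log-SD, share of zeros, and a USD 5,000 mean as a low-cost case. The simulations compare two groups with no true difference and no covariates, using 1,500 to 3,000 replicates. Ranges are across separate runs.

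**The plan's own figure.** The plan gives none for the cost models. Its one design figure reproduces: (1.960 + 0.842) × √(2/75) = 0.457, or 0.4605 with the noncentral t, against the stated d = 0.46. It concerns a difference in means with equal SDs and says nothing about skewed costs.

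**Formula.** With a log link and two groups, the model-based variance of the log cost ratio is the sum over groups of (1/μ + α)/n. The true sampling variance is approximately the sum of CV²/n. The standard error is right when 1/μ + α = CV².

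**Positive costs at the documented scale.** At μ = 250,000, 1/μ = 0.000004, so the negative binomial is numerically a gamma model. Its standard error exceeds the gamma one by √(1 + 1/(αμ)): at most 1.00001 in dollars and 1.008 in thousands, for α from 0.25 to 2.25. One simulated dataset gave p = 0.0734 in cents, 0.0734 in dollars and 0.0730 in thousands. The unit matters only when the rescaled mean is small. In millions (mean 0.25) the same data gave p = 0.343, and type I error fell to 0.0–0.9%; the underdispersion correction in SAP 6.1.3 restored it to 4.9–6.6%.

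**Gamma-shaped costs, dollars, estimated dispersion.** At CV 0.5, 1.0 and 1.5, mean standard errors were 0.0809, 0.1625 and 0.2432 against empirical SDs of 0.0806, 0.1634 and 0.2426. Type I error was 4.9%, 5.6% and 4.9%. These standard errors are correct.

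**Lognormal costs, dollars, estimated dispersion.** At this scale the likelihood sets α = 1/k, where log k − ψ(k) = s²/2 and s is the log-SD. The true CV² is exp(s²) − 1. The standard error is too small by √(α/CV²), and the approximate type I error is 2Φ(−1.96 × that ratio):

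| s | α | CV² | SE ratio | approx. type I | simulated |
|---|---|---|---|---|---|
| 0.5 | 0.240 | 0.284 | 0.920 | 7.1% | 6.8–7.9% |
| 0.8 | 0.585 | 0.897 | 0.808 | 11.3% | 10.8–12.1% |
| 1.0 | 0.879 | 1.718 | 0.715 | 16.1% | 15.2–16.4% |
| 1.2 | 1.217 | 3.221 | 0.615 | 22.8% | 19.2–21.6% |

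Sandwich standard errors on the same mean model gave about 5–8%. The underdispersion correction did not help, because it can only shrink standard errors.

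**Cause.** On lognormal data with CV 0.5, 1.0 and 1.5, a gamma model with maximum-likelihood scale gave 7.3%, 13.5% and 16.9%, identical to the negative binomial on the same data. In a separate run, a gamma model with Pearson scale gave 6.0%, 5.7% and 6.4%, against 7.8%, 12.0% and 18.0% for the negative binomial. The fault lies in likelihood-based dispersion without a robust or Pearson-scaled standard error, not in the count family alone.

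**Some zero costs, s = 1.0.** With a USD 5,000 mean before zeros and 20% zeros, the true CV² is 2.718/0.8 − 1 = 2.40. The model's probability of a zero is (1 + αμ)^(−1/α). Matching 20% needs α ≈ 6.3 at μ = 4,000 (dollars) but α = 1 at μ = 4 (thousands, where 5⁻¹ = 0.20). The fitted α is a compromise between the zeros and the positive costs, but it is pulled above the true value in one unit and below it in the other. Simulated type I error:

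| scenario | dollars | thousands |
|---|---|---|
| USD 5,000 mean, 20% zeros | 1.0–1.5% | 10.6–11.3% |
| USD 250,000 mean, 5% zeros | 5.5–6.4% | 9.7–10.9% |

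Sandwich standard errors gave 6.2–7.1% in these four cells in one run. The underdispersion correction brought the 1.5% cell to 6.8% but left the 10.6% cell unchanged.

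**If software fixed α at 1.** The standard error would be √(2/75) = 0.1633 whatever the CV. For gamma costs, type I error would be 0.0%, 5.5% and 18.2% at CV 0.5, 1.0 and 1.5. SAP 6.1.3 implies an estimated dispersion but names no method.

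**The case against.** SAP 6.1.3 lets the outcome's distribution decide the family, calls for fits to be examined, implies an estimated dispersion and corrects for underdispersion. SAP 6.2.3 itself speaks of an appropriate distribution. An analyst following the spirit of that text could reach a sound cost model. Section 6.2.2 also allows cost comparisons to be replaced by descriptive statistics if few patients supply claims. And every participant must infuse at least three times a month, so frequent zeros in drug costs are unlikely.

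Much of this stands. It rules out the reading that the standard errors are wrong simply because costs are not counts: with positive gamma-shaped costs in dollars they are right, and a gamma model with likelihood-based scale would share the heavy-tail problem. It also rules out a general claim of unit dependence, which is immaterial at the documented scale without zeros.

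It does not close the gap. The only families named for skewed data are count models, 6.2.3 applies one of them to costs explicitly, and the one correction cannot widen a standard error that is too small. Zeros remain possible in non-drug costs. They may also arise in claims-based drug costs, since Table 2 records patient-assistance programs and separate pharmacy insurers, and Protocol 8.4 expects claims to differ in content between insurers.

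**Conclusion.** The cost model is inapt and underspecified, and following 6.2.3 as written can give wrong cost p-values. With lognormal tails, type I error is about 8% to 20% at nominal 5% (75 per group, mean USD 250,000, log-SD 0.5 to 1.2). With zero costs and log-SD 1.0 it also moves with the unit: about 1% against 11% (USD 5,000, 20% zeros) and about 6% against 10% (USD 250,000, 5% zeros), dollars against thousands.

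A reader might infer that the cost p-values cannot be trusted at all. The documents do not support that: they give no cost SD, tail shape or zero share, and under benign conditions the planned standard errors are correct. Confidence is moderate, because the size rests on those assumptions. The change should be made, but the flaw is not fatal to the study.

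**What to change.** In SAP 6.2.3, and in 6.1.3 for consistency:

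- Keep the negative binomial for visit counts only.
- For costs, specify a log-link GLM with gamma-type (quasi) variance and sandwich or Pearson-scaled standard errors. The standard error is the essential part; changing the family while keeping a likelihood-based scale would leave the heavy-tail inflation in place.
- State how zero costs are handled, with a two-part model if they are common and a definition of common fixed in advance. State the currency unit as well.
- In Table 8, report the adjusted cost ratio or difference between treatment groups with its 95% interval, beside the group means.

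This costs a few lines of SAP text and standard software options, with no new data. Intervals may be somewhat wider. Type I error would still be about 5–8% at this sample size, and reached 9% in the worst zero-cost case simulated.
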